10.10. PHYSICAL EXAMINATION

Physical examination results will be listed by age group, group/cohort, subject and visit.

Missing data will not be imputed.

10.11. ASSESSMENT OF ASTHMA CONTROL

Assessment of asthma control in asthmatic subjects using the Asthma Control Test (ACT) questionnaire will be performed.

For subjects 12 years old or older, the ACT has 5 questions each recorded on a scale of 1 (least control) to 5 (greatest control). The total ACT is the sum of the 5 scores and ranges from 5 (least control) to 25 (greatest control). A total score of 19 or less indicates asthma is not adequately controlled. Missing data will not be imputed. If any of the 5 questions have a missing response, the total ACT score will not be calculated.

For subjects under 12, there are 4 questions for the subject and 3 questions for the parents to complete. Subject responses range from 0 (least control) to 3 (greatest control). Parent responses range from 0 (every day) to 5 (no days). The sum of all 7 questions will make up the total score. The total ACT score for subjects under 12 will range from 0 (least control) to 27 (greatest control). A total score of 19 or less indicates asthma is not adequately controlled. Missing data will not be imputed. If any of the questions have a missing response, the total ACT score will not be calculated for that subject.

All analyses of the ACT will be performed separately by subject age group (4-11 for subject and parent, 12-17 subjects). Summary statistics of the score for question, total score and change from baseline will be tabulated by visit and group/cohort. A shift table of asthma control (adequate, not adequate, missing) will be summarized by group/cohort at each visit. The number of subjects with completed ACT questionnaires will be used as the denominator for all percentages.

Listing of the results from the questionnaire, including the total score, will be provided, sorted by age group, group/cohort, subject, and visit.

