7.5. DATA DERIVATIONS AND DEFINITIONS

The following definitions and derivations will be used throughout this study:

- Study day is calculated relative to the first dose date in ARC004 as (assessment date – first dose date + 1) for assessments and visits performed on or after the first dose date, and (assessment date – first dose date) for assessments and visits prior to the first dose date.
- In this follow on study, baseline is defined as the last non-missing value prior to the first dose of study treatment in the study where study product is first received. For Group 1 patients (those previously on placebo in ARC003), baseline is relative to first dose of AR101 in study ARC004. For Group 2 patients (those continuing on AR101 therapy from ARC003), baseline is relative to first dose of AR101 in study ARC003. If no ARC004 data were entered for a Group 1 subject, use the last available ARC003 data prior to first dose of AR101 in ARC004. For food challenge end points, the ARC003 exit food challenge will serve as the baseline for both groups.

Sponsor: Aimmune Therapeutics, Inc.

Protocol: ARC0004

Version: Version 1.0, 10Jul2019

- Change from baseline is calculated as observed value after the first dose – baseline value.
- Group 1 Initial Dose Escalation period is defined as the time period beginning with the date and time of the first dose of study product in clinic and ending with the date of the last dose of study product taken prior to Up-dosing.
- Group 1 Up-dosing period is defined as the time period beginning with the date and time of the first home dose of study product at 3 mg, and ending with the date and time of first in-clinic dose at 300 mg. This period will be, ideally, 22 weeks in duration, but may be extended to a maximum of 40 weeks to accommodate dose reductions and re-escalations, if necessary.
- Group 1 Maintenance period is defined as the time period beginning with the date and time of the first home dose of study product at 300 mg and ending with the date of the last dose of study product taken prior to the maintenance DBPCFC. The maintenance period lasts approximately 24 weeks.

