8.3. DEMOGRAPHIC AND OTHER BASELINE CHARACTERISTICS

Summary statistics for demographic and baseline characteristics will be provided for the Safety population summarized by age group (ages 4-17, 18-55) and group/cohort (Group 1, Group 2 Cohort 1, Group 2 Cohort 2, Group 2 Cohort 3A, Group 2 Cohort 3B, Group 2 Cohort 3C, and Total).

Demographic data will include age, sex, country, ethnicity, race, height, body weight, and body mass index (BMI). Baseline characteristics include total IgE, ps-IgE, ps-IgG4, ps-IgE/IgG4 ratio, SPT mean wheal diameter at screening, MTD of peanut protein at ARC003 Exit DBPCFC, childbearing potential, method of birth control, and history of asthma.

Demographic characteristics that cannot change over time (e.g., race) are summarized as collected in ARC003.

Age will be calculated relative to date of informed consent for the ARC004 study, as follows:

- If the month and day portion of the informed consent date is prior to the month and day portion of the birthdate, age will be calculated as the year of informed consent minus the year of birth, minus one;

Sponsor: Aimmune Therapeutics, Inc.

Protocol: ARC0004

Version: Version 1.0, 10Jul2019

- If the month and day portion of the informed consent date is on or after the month and day portion of the birthdate, age will be calculated as the year of informed consent minus the year of birth.

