9.1.7. Quality of Life Assessments

Quality of life assessment using the FAQLQ and the FAIM questionnaires will be performed prior to the start of treatment and after the Exit DBPCFC or early discontinuation.

Separate FAQLQ and FAIM instruments are administered based on the subject's age group. Parent versions are also administered for all subjects. Due to differences between the various instruments, separate summaries will be provided by age group and person who completed the questionnaire (i.e., subject or parent).

FAQLQ:

The FAQLQ is a self-report instrument that is intended to assess the effect of food allergy on the subject's quality of life. Evaluations are done by the subject using a different form by age group (8-12 years and 13-17 years) ([Flokstra-de Blok, 2008](#); [Flokstra-de Blok,](#)

Sponsor: Aimmune Therapeutics, Inc.

Protocol: ARC0004

Version: Version 1.0, 10Jul2019

[2009](#)). Evaluations are also done by the parent/caregiver using a different form by age group (4-6 years, 7-12 years, and 13-17 years) ([DunnGalvin, 2008](#)).

Each question is presented on a scale from 0 (not at all) to 6 (extremely) and scored from 1 to 7. The number of items and domains varies by instrument administered. For reporting, the domains for each included form are as follows:

Adult form ≥ 18 –

- a) Allergen Avoidance and Dietary Restrictions
- b) Risk of Accidental Exposure
- c) Emotional Impact
- d) Food Allergy Related Health

Teen form 13-17 –

- a) Allergen Avoidance and Dietary Restrictions
- b) Risk of Accidental Exposure
- c) Emotional Impact

Child form 8-12 –

- a) Allergen Avoidance and Dietary Restrictions (Allergen Avoidance + Dietary Restrictions)
- b) Risk of Accidental Exposure
- c) Emotional Impact

Parent form teen 13-17 –

- a) Social and Dietary Limitations (Dietary Restrictions + Social Restrictions)
- b) Food Anxiety
- c) Emotional Impact

Parent form 7-12 –

- a) Social and Dietary Limitations
- b) Food Anxiety
- c) Emotional Impact

Parent form 4-6 –

- a) Social and Dietary Limitations
- b) Food Anxiety
- c) Emotional Impact

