For each domain, the domain average score is the arithmetic average of the non-missing items comprising the domain. For any respondent and form, the domain score algorithms above should be derived only if more than half the items comprising that domain score have valid responses. For all forms, the total score will be calculated as the average of the domain averages: (average a + average b + average c) / 3. Total scores should not be

Sponsor: Aimmune Therapeutics, Inc.

Protocol: ARC0004

Version: Version 1.0, 10Jul2019

computed if one or more of the domain scores comprising the total are missing. For FAQLQ-PF 4-6, if items are completed that were not included for this age group, these items will not be included towards the scoring. For FAQLQ-AF, the fourth domain of Food Allergy Related Health is not included in the total score calculation.

For child, teen, and all parent forms, descriptive statistics on the total and domain scores along with their changes from baseline will be provided. Data will be summarized for the safety population separately by questionnaire age group and responder (subject or caregiver).

Listing of the raw scores as recorded in the CRF, domain scores, and total scores will be provided, sorted by age group, group/cohort, and subject ID.

FAIM:

The FAIM is a self-report instrument that is intended to reflect the perception of food allergy severity and related risk as evaluated by the subject using a different form by age group (8-12 years and 13+ years) ([van der Velde, 2010](#)). Evaluations are also done by the parent/caregiver using a different form by age group (4-12 years and 13-17 years). The instrument consists of 6 questions (4 expectation of outcome questions and 2 disease severity questions). The parent/caregiver versions include questions related to perception of disease severity and expectation of allergen exposure outcome. The parent/caregiver form includes 8 questions for subjects aged 4-12 years and 4 questions for subjects aged 13 to 17 years.

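### The SAP's change from baseline in ACT, FAQLQ and FAIM has no same-form condition, so a child who moves to another age form can have scores from two different forms subtracted, with a change of scale for the ACT

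*SAP*

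**What the plan says.** **Change and baseline.** SAP 7.5 gives one definition of change for the whole study, observed value minus baseline value, and attaches no condition about the form used. On baseline it says: "For Group 2 patients (those continuing on AR101 therapy from ARC003), baseline is relative to first dose of AR101 in study ARC003". For Group 1 the reference is the first AR101 dose in ARC004.

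**ACT (SAP 10.11).** From age 12: "The total ACT is the sum of the 5 scores and ranges from 5 (least control) to 25 (greatest control". Below 12: "The total ACT score for subjects under 12 will range from 0 (least control) to 27 (greatest control". The lower-age form has four child items and three parent items. For both forms, "A total score of 19 or less indicates asthma is not adequately controlled". Change from baseline is tabulated by visit and group/cohort, with a shift table of adequate against inadequate control. On age the section says: "All analyses of the ACT will be performed separately by subject age group (4-11 for subject and parent, 12-17 subjects". It does not say whether this is age at baseline, at consent or at the visit. The SAP's one age definition is in 8.3, on demographics: "Age will be calculated relative to date of informed consent for the ARC004 study".

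**FAQLQ and FAIM (SAP 9.1.7).** "Separate FAQLQ and FAIM instruments are administered based on the" subject's age group, and summaries are kept apart by questionnaire age group and by respondent. Items score 1 to 7 on every form. For the FAQLQ child, teen and parent forms, "descriptive statistics on the total and domain scores along with their changes from baseline will be provided"; FAIM changes are tabulated likewise. No sentence covers a child whose baseline and exit forms differ.

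**The concern.** Sorting by the subject's age is not the same as sorting by form. Take a Group 2 child aged 11 at the ARC003 baseline and 12 at ARC004 consent. If 10.11 uses consent age, this child is in the 12-17 table with a baseline on the 0-27 form and follow-up on the 5-25 form. If it uses baseline age, the same child is in the 4-11 table with the same mismatched pair. Under either date, the rule in 7.5 subtracts a score on one scale from a score on another. Group 1 children who turn 12 during ARC004 meet the same problem.

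Change in asthma control and change in quality of life are both named secondary endpoints (SAP 3.2), and ages 4-17 are the main reporting group (SAP 6.3). Part of a reported mean change could then come from the switch of form. The alternatives of dropping switchers, or keeping each child on the starting form, give different tables, and the SAP does not choose among them.

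**Working it through.** **1. ACT ranges, from the items in SAP 10.11.**
- From age 12: 5 × 1 = 5 to 5 × 5 = 25.
- Under 12: 0 to 4 × 3 + 3 × 5 = 27.

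Both stated ranges reproduce.

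**2. Size of the artefact for one child.** Put a child at the same fraction p of each range. The under-12 score is 27p and the later score is 5 + 20p, so the apparent change is (5 + 20p) - 27p = 5 - 7p.

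| Position | p | Apparent change |
|---|---|---|
| Floor | 0 | +5 |
| Middle | 0.5 | +1.5 |
| Under-12 score of 19 | 19/27 = 0.704 | +0.07 |
| Ceiling | 1 | -2 |

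On the older form the cut of 19 lies at (19 - 5)/20 = 0.70 of the range, almost the same place. The shift table is therefore little affected.

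**3. Time from baseline to exit, Group 2.** ARC003's length is an assumption, taken from the matching Group 1 schedule: 22-40 weeks of up-dosing plus about 24 of maintenance, or 46-64 weeks. ARC004 adds 28 weeks (Cohorts 1 and 2) or 56 weeks (3A and 3B).
- Cohorts 1 and 2: 74-92 weeks, or 1.42-1.76 years (52.18 weeks per year).
- Cohorts 3A and 3B: 102-120 weeks, or 1.95-2.30 years.

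Cohort 3C was planned at 84 weeks. SAP 6.1 says no subject started weekly dosing, so I do not rely on that length.

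**4. Share of under-12 subjects who switch ACT form.** The documents give no age distribution. With uniform ages, the share is elapsed years divided by the 8-year band (ages 4-11).
- Cohorts 1 and 2: 1.42/8 to 1.76/8 = 18-22%.
- Cohorts 3A and 3B: 1.95/8 to 2.30/8 = 24-29%.
- Group 1, at its planned 88-136 weeks (1.69-2.61 years): 21-33%. This length included interval extension, and SAP 2.3 now keeps Group 1 subjects who are on daily dosing on it, so the actual length may differ.

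**5. Shift in a Group 2 mean, every child at the ceiling (-2 each).** Sorted by age at ARC004 consent:
- Ages 12-17, baseline on the under-12 form: 46-64 weeks over a 6-year band = 0.88/6 to 1.23/6 = 15-20%, a shift of -0.3 to -0.4.
- Ages 4-11, turning 12 after consent: 28 weeks gives 0.54/8 = 6.7% and -0.13; 56 weeks gives 1.07/8 = 13.4% and -0.27.

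Sorted by baseline age instead, all switchers fall in the under-12 rows: 18-29% × -2 is about -0.4 to -0.6.

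**6. FAQLQ and FAIM.** The narrowest form is the parent FAQLQ for ages 4-6 (3 years). With baseline before ARC003 dosing, 1.42/3 to 1.76/3 = 47-59% would switch in Cohorts 1 and 2, and 1.95/3 to 2.30/3 = 65-77% in 3A and 3B. Protocol Appendix 1 also schedules these questionnaires around the ARC003 exit challenge. If that one served as baseline, the shares would be 0.54/3 = 18% and 1.07/3 = 36%.

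**The case against.** The strongest reply is that no sentence orders scores from different forms to be subtracted. The age split in 10.11 is a partial safeguard, and 9.1.7 goes further by separating summaries by questionnaire age group and respondent. The consent-age rule stands in the demographics section, so applying it to the ACT is inference. The numerical effect is also small. Severe asthma, and mild or moderate asthma that is uncontrolled or hard to control, are excluded (Protocol Appendix 7), so the +5 floor case is unrealistic. The ACT applies only to subjects with asthma, whose number is not given. No formal comparisons are planned (SAP 6.4).

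Most of this stands, and it limits the point. For FAQLQ and FAIM, a reader might infer a change of scale like that of the ACT. The documents do not support that: items score 1-7 on every form, the FAQLQ child and teen forms report the same three domains, as do the three parent forms, and the FAIM child and teen forms list the same domains. What remains is that item content varies by form, that the FAIM parent form goes from two domains to one at 13, and that nothing says which table holds a switcher's change.

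A reader might also infer bias between daily and nondaily cohorts. Cohorts 1 (daily) and 2 (nondaily) both last 28 weeks, and randomized 3A (daily) and 3B (nondaily) both last 56, so planned crossing time is equal within each pair.

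The reply does not remove the ACT problem. The change rule in 7.5 is general, and a split on one age date, whichever it is, leaves mismatched pairs among children who turn 12 between baseline and follow-up.

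**Conclusion.** The point holds for the ACT: as written, the SAP allows a baseline on one form to be subtracted from follow-up on another, and the age split does not prevent it. It would go too far to say that the SAP plans this subtraction; it gives a general rule and no exception.

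Switching could be common (18-22% of under-12 subjects in Cohorts 1 and 2, 24-29% in 3A and 3B), but the effect on means is modest: about -0.1 to -0.4 points in Group 2 with consent-age sorting and every child at the ceiling. These figures rest on uniform ages, a 46-64 week ARC003 and forms given by current age. The shares describe all children, not only those with asthma.

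For FAQLQ and FAIM the gap is a missing pairing rule across forms with different items. Its extent depends on which ARC003 questionnaire is the baseline.

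**What to change.** In SAP 9.1.7 and 10.11:

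- State that change from baseline is computed only when baseline and follow-up used the same form and the same respondent.
- Define the age date, or preferably the form, that places a subject in a table.
- Report the number of form switchers by group and cohort for each instrument.
- For ACT switchers, rely on the shift table of adequate and inadequate control that 10.11 already plans, since the cut of 19 lies at about 0.70 of both ranges.

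The same-form rule makes the artefact zero by construction. The work is a few sentences and a form-version check in programming. The cost is fewer subjects in the mean-change rows, and those lost are the oldest children within each form, which the switcher counts will show.

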10.12. ASSESSMENT OF GI SYMPTOMS BY PEES

Subjects who discontinue treatment due wholly or in part to GI AEs will be instructed to complete the Pediatric Eosinophilic Esophagitis Symptom Scores (PEESS v2.0)

Sponsor: Aimmune Therapeutics, Inc.

Protocol: ARC0004

Version: Version 1.0, 10Jul2019

questionnaire ([Martin, 2015](#); [Franciosi, et al., 2011](#)) monthly for 6 months.

The PEESs questionnaire is composed of 20 items investigating the frequency and severity of eosinophilic esophagitis (EoE) symptoms in the last month. The total score consists of all 20 items. The frequency of symptoms is assessed by items 1, 3, 5, 7, 9, 11, 13, 15, 17, 19 and 20, where each item is scored as: 0=Never, 1=Almost never, 2=Sometimes, 3=Often, 4=Almost always. The severity of symptoms is assessed by items 2, 4, 6, 8, 10, 12, 14, 16, and 18, where each item is scored as: 0=Not bad at all, 1=A little bad, 2=Kind of bad, 3=Bad, 4=Very bad. Each item score is transformed to 0-100 as follows: 0=0, 1=25, 2=50, 3=75, 4=100.

The total, frequency total, and severity total scores are computed as the sum of the items divided by the number of items answered. If more than 50% of the items for the calculation of a score are missing, the score will not be calculated.

PEESS results including the frequency total, severity total, and total scores, will be listed.

10.13. EPINEPHRINE USE AS RESCUE MEDICATION

Epinephrine use is defined as any rescue medication with a preferred name of 'EPINEPHRINE' when coded as described in [Section 10.2](#).

All subjects, per protocol, are required to have epinephrine autoinjectors for use in case of a suspected anaphylactic reaction occurring outside of the clinic. There are, however, differences in how, and even if, physicians record the prescription of epinephrine autoinjectors for as-needed (PRN) use. As a consequence of this, the presence or absence of a PRN prescription for epinephrine cannot be taken to indicate epinephrine usage, regardless of whether the prescription was written prior to, or after, enrollment in the study. What is important is to be able to quantitate the number of subjects receiving doses of epinephrine and the number of doses. As epinephrine should only be administered to treat a discrete allergic reaction, each dose of epinephrine should be closely temporally associated with a specific safety event and its use recorded on the Rescue Medication CRF form. In cases where a PRN epinephrine prescription is issued after the start of study-product dosing, the sites will be queried as to if, and when, epinephrine was actually administered and to treat what specific event.

All epinephrine use will be listed for the Safety population.

In addition, epinephrine use excluding food challenges will be summarized by group/cohort and study period. The total number and percent of subjects with any episode, the number and percent of subjects with at least 1 episode, where episode refers to 1 or more doses of epinephrine within a 2-hour window, will be summarized as well as the number of episodes experienced by each subject (1, 2, 3, and > 3). For these subjects, demographics including age, age category, baseline PS IgE, and baseline PS IgE category will be included. The total number of episodes will also be presented along with the number and percent of episodes by number of doses per episode, by associated adverse

Sponsor: Aimmune Therapeutics, Inc.

Protocol: ARC0004

Version: Version 1.0, 10Jul2019

event severity, by seriousness of associated adverse events, by relatedness of associated adverse events, and by location of episode (home/study site). For subject counts, the number of subjects at risk within each study period will be used as the denominators. For unique episode counts, the total number of episodes within each study period will be used as the denominators.

